**Figure 1. Study Schematic**

Non-ventilated participants will take study drug orally. Ventilated participants will receive study drug through a nasogastric (NG) or nasoenteric (NE) tube. Once participants are discharged from the hospital, they will no longer be administered study drug.

Successful treatment of ARDS associated with COVID-19 will likely require co-administration of drugs with complementary mechanisms of action targeting different components of the disease, such as antiviral compounds to control viral replication (e.g., remdesivir) combined with drugs with the potential to address the pathophysiology of ARDS, in addition to respiratory support measures. Therefore, treatment with investigational COVID-19 therapies available under EUA by the FDA may be allowed, pending review and approval by the Medical Monitor and Sponsor Study Director. Key considerations for allowing co-administration of PLN-74809 with investigational COVID-19 therapies under EUA will include the potential for drug interactions and adverse drug reactions. Treatment with off-label use of any other drugs, devices, or interventions that might be used to manage COVID-19 may also be allowed, pending review and approval by the Medical Monitor and Sponsor Study Director.

Participants who discontinue study drug for regardless of reason prior to completion of up to 14 days of treatment will be encouraged to remain in the study to complete all remaining assessments until hospital discharge or Day 28, whichever is sooner. If this is not feasible, they will be asked to perform an Early Termination (ET) visit for follow-up evaluations.

### 3.2 Rationale for Study Design and Control Group

[REDACTED]

[REDACTED]

[REDACTED]

[REDACTED]

[REDACTED]

### **3.3 Study Duration**

Each participant will participate in the study for up to approximately 107 days, including screening, treatment, and post-treatment follow-up. The end of study is defined as the last visit of the last randomized participant.

The planned duration of treatment is at least 7 days and up to 14 days or until day of hospital discharge, whichever is less. Once participants are discharged from the hospital, they will no longer be administered study drug.

## 4 STUDY POPULATION AND SELECTION

### 4.1 Study Population

Participants with ARDS associated with at least severe COVID-19 who meet with the following eligibility criteria may be enrolled.

Treatment with investigational COVID-19 therapies available under EUA by the FDA and/or off-label use of any other drugs, devices, or interventions that might be used to manage COVID-19 may be allowed, pending review and approval by the Medical Monitor and Sponsor Study Director.

#### 4.1.1 *Inclusion Criteria*

Each participant must meet all the following criteria to be enrolled in the study.

##### General and Administrative

1. Ages 18 years and older.
2. Able to provide consent either on their own behalf or through a legally authorized representative.
3. Female participants of childbearing potential (ovulating or premenopausal and not surgically sterile) and male participants with sexual partners of childbearing potential must agree to use highly effective methods of birth control during their participation in the study and for 30 days for female participants and 90 days for male participants and female partners of male participants after the last administration of study drug. Highly effective methods of birth control are defined as those with 99% or greater efficacy (see [Section 6.7.4](#)).
4. Female participants of nonchildbearing potential must be either surgically sterile (defined as hysterectomy, bilateral tubal ligation, salpingectomy and/or bilateral oophorectomy at least 6 months prior to screening) or postmenopausal (defined as 12 months of spontaneous amenorrhea without an alternative medical cause or 6 months of spontaneous amenorrhea with serum follicle-stimulating hormone [FSH] levels >40 mIU/mL)
5. Agree to abstain from sperm or egg donation through 90 days or 30 days, respectively, after administration of the last dose of study drug.
6. [REDACTED]

### ARDS Diagnosis

7. Clinical diagnosis of ARDS, as defined by Berlin criteria (refer to [Appendix 2](#)), including:
  - a. Chest imaging (radiography or CT scan): bilateral opacities not fully explained by effusions, lobar/lung collapse, or nodules
  - b. Origin of edema: respiratory failure not fully explained by cardiac failure or fluid overload
  - c. Acute hypoxemia defined by partial pressure of arterial oxygen (PaO2)/ fraction of inspired oxygen (FiO2):
    - i. Mild hypoxemia: 200 mm Hg < PaO2/FiO2 ≤ 300 mm Hg with positive end-expiratory pressure (PEEP) or continuous positive airway pressure (CPAP) ≥ 5 cm H2O
    - ii. Moderate hypoxemia: 100 mm Hg < PaO2/FiO2 ≤ 200 mm Hg with PEEP ≥ 5 cm H2O
    - iii. Severe hypoxemia: PaO2/FiO2 ≤ 100 mm Hg with PEEP ≥ 5 cm H2O

**Note:** If a reliable estimation of FiO2 is not possible in non-ventilated participants, those meeting inclusion Criteria 9 and 10 will be eligible if all other criteria are met.

8. The radiological and hypoxemia inclusion criteria (i.e., 7a and 7c) must be met within the same 24-hour period. The time of onset of ARDS is defined as the time when these two criteria are met.
9. Receiving support for acute lung injury/respiratory distress via supplemental oxygen (e.g., high flow nasal cannula [HFNC], face mask [i.e., non-rebreather]), non-invasive ventilation, or via intubation and mechanical ventilation.

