### 2.3 Exploratory Objectives

### 3 INVESTIGATIONAL PLAN

#### 3.1 Overall Study Design and Plan

[figure not shown]
This is a Phase 2a, multicenter, randomized, double-blind, dose-ranging, placebo-controlled, study to evaluate the safety, tolerability, and PK of treatment with PLN-74809 for at least 7 and up to 14 days in participants with ARDS associated with at least severe COVID-19. The study will include an up to 3-day screening period, a 7- to 14-day (or day of hospital discharge, whichever one is sooner) treatment period, and a 90-day follow-up period (Figure 1).

Approximately 36 participants will be enrolled sequentially into 3 cohorts. Within each cohort of 12 participants, 9 will be randomized to PLN-74809 and 3 will be randomized to placebo (3:1 ratio).

- In Part 1, approximately 12 participants will be randomized to 40 mg PLN-74809 or placebo QD
- In Part 2, approximately 12 participants will be randomized to 80 mg PLN-74809 or placebo QD
- In Part 3, approximately 12 participants will be randomized to 160 mg PLN-74809 or placebo QD

A DSMB will be established to assess participant safety at predetermined intervals during the study, and as needed (refer to [Section 14.7](#)). [REDACTED]

Commencement of Part 2 and Part 3 will occur only following favorable data safety monitoring board (DSMB) review of the previous study part. The 160 mg cohort will only be dosed following favorable DSMB review of the 80 mg cohort. [REDACTED]

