##### **ARDS Status**

1. Greater than 72 hours since time of onset of ARDS.
2. Greater than 7 days since start of mechanical ventilation.
3. Unwillingness to follow lung protective ventilation strategy (i.e., tidal volume of 6 mL/kg of predicted body weight and prone positioning) and fluid management protocol (Fluids and Catheters Treatment Trial [FACTT] Conservative or Lite) per local institutional standards. See [Appendix 3](#) for further details.
4. Currently receiving or anticipated to receive extracorporeal life support (ECLS), extracorporeal membrane oxygenation (ECMO) or high-frequency oscillatory ventilation (HFOV).

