### 7.2 Inclusion/Exclusion Criteria

The inclusion/exclusion criteria will be reviewed at the screening and baseline (Day 1) visits. Potential participants must meet all of the inclusion criteria ([Section 4.1.1](#)) and none of the exclusion criteria ([Section 4.1.2](#)) to be enrolled in the study.

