## APPENDIX 2. BERLIN DEFINITION OF ARDS

ARDS	
Timing	Within 1 week of a known clinical insult or new or worsening respiratory symptoms
Chest imaging a	Bilateral opacities – not fully explained by effusions, lobar/lung collapse, or nodules
Origin of edema	Respiratory failure not fully explained by cardiac failure or fluid overload Need objective assessment (e.g., echocardiography) to exclude hydrostatic edema if no risk factor present
Oxygenation b	
Mild	$200 \text{ mm Hg} < \text{PaO}_2/\text{FiO}_2 \leq 300 \text{ mm Hg}$ with PEEP or CPAP $\geq 5 \text{ cm H}_2\text{O}^c$
Moderate	$100 \text{ mm Hg} < \text{PaO}_2/\text{FiO}_2 \leq 200 \text{ mm Hg}$ with PEEP $\geq 5 \text{ cm H}_2\text{O}$
Severe	$\text{PaO}_2/\text{FiO}_2 \leq 100 \text{ mm Hg}$ with PEEP $\geq 5 \text{ cm H}_2\text{O}$

CPAP = continuous positive airway pressure; FiO2 = fraction of inspired oxygen; PaO2 = partial pressure of arterial oxygen; PEEP = positive end-expiratory pressure.

a Chest radiograph or CT scan

b If altitude is higher than 1000 m, the correction factor should be calculated as follows:  
[PaO2/FiO2 × (barometric pressure/760)]

c This may be delivered noninvasively in the mild ARDS group

Source: [REDACTED]

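### Does the route for participants without a reliable FiO2 leave the 72-hour ARDS limit without a starting time, so that the plan must change?

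*Protocol*

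**What the plan says.** Criterion 7 of Protocol 4.1.1 requires ARDS by the Berlin criteria: bilateral opacities on imaging (7a), edema not explained by a cardiac cause or fluid overload (7b), and hypoxemia (7c). 7c is expressed only as PaO2/FiO2 bands with a minimum airway pressure.

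A Note beneath it deals with non-ventilated participants whose FiO2 cannot be estimated reliably: "those meeting inclusion Criteria 9 and 10 will be eligible if all other criteria are met". Criterion 9 is current respiratory support. Criterion 10 is hospitalization with at least severe COVID-19, shown by a positive test, symptoms and clinical signs.

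Criterion 8 then says: "The radiological and hypoxemia inclusion criteria (i.e., 7a and 7c) must be met within the same 24-hour period". It continues: "The time of onset of ARDS is defined as the time when these two criteria are met". Exclusion 1 in 4.1.2 removes anyone with "Greater than 72 hours since time of onset of ARDS". The lead-in to 4.1.1 says "Each participant must meet all the following criteria to be enrolled in the study". The synopsis repeats the Note, criterion 8 and exclusion 1.

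Eligibility is checked twice: "The inclusion/exclusion criteria will be reviewed at the screening and baseline (Day 1) visits". On timing, Protocol 3.1 says: "The study will include an up to 3-day screening period".

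**The concern.** The Note applies exactly when 7c cannot be evaluated, yet criterion 8 needs 7c both for its 24-hour window and for the onset time. Neither refers to the other. Read strictly, a participant using the Note fails criterion 8, so the Note would admit nobody. Read as the Note evidently intends, the participant can enter, but nothing states when the hypoxemia element is met.

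At stake is exclusion 1, which limits how long after onset a participant may enter. If its starting point is undefined, two sites could classify the same participant differently, one as eligible and the other as excluded or as a protocol deviation. No bias between arms is suggested: eligibility is settled before or at the Day 1 visit, where blinded randomization takes place, so any ambiguity falls on both arms alike.

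**Working it through.** **Is an onset time given elsewhere?**

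- Criteria 9 and 10 describe states and findings. They carry no time and no link to onset.
- Exclusion 2 counts from the start of mechanical ventilation, but the Note concerns non-ventilated participants.
- The timing row of Protocol Appendix 2 ("Within 1 week of a known clinical insult or new or worsening respiratory symptoms") is the interval from insult to ARDS. It is a different clock.
- SAP 4.6 derives study day, baseline and shift from baseline, not ARDS onset.

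So the readable text has no other definition of onset.

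**How much of exclusion 1 does this affect?**

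Inputs: the 24-hour window (criterion 8), the 72-hour limit (exclusion 1) and screening of up to 3 days = 72 hours (3.1). Assumption: one qualifying image.

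Let A be the age of the image in hours at the eligibility check, and d the hours from image to hypoxemia element (negative if hypoxemia came before the image). Onset is when both elements are met, which is the later of the two, so

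onset age = min(A, A − d), with |d| ≤ 24 under criterion 8.

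If criteria 9 and 10 take the place of 7c and the window is kept:

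| Image age A | Onset age over all allowed d | Exclusion 1 |
|---|---|---|
| A ≤ 72 | never above A, so at most 72 | passes for every d |
| 72 < A ≤ 96 | from A − 24 (at most 72) to A (above 72) | depends on the undefined time |
| A > 96 | at least A − 24, so above 72 | fails; a d above 24 fails criterion 8 instead |

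The upper edge is 72 + 24 = 96 hours. The missing time therefore matters only in a band 24 hours wide.

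**Can the band be reached?** Yes. An image taken 20 hours before a full 72-hour screening period gives A = 20 + 72 = 92.

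- d = 19: onset age 92 − 19 = 73 hours, excluded.
- d = 21: onset age 92 − 21 = 71 hours, eligible.

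This is a corner case. It uses the whole screening period, and the eligible branch places the hypoxemia element 21 − 20 = 1 hour after screening began.

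**If the 24-hour window is waived together with 7c:**

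- Criteria 9 and 10 still supply an untimed second element: every A > 72 is undetermined.
- 7c simply drops out, leaving imaging as the only element of criterion 8: onset can be read as the imaging time, and A > 72 is excluded.

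On every reading that gives the Note effect, A ≤ 72 passes.

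**Which planned outputs depend on it?**

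- Analysis sets (Protocol 12.3, SAP 4.2): the Safety Set is everyone randomized and dosed; the PK set adds a measurable concentration. Neither uses eligibility.
- Testing (Protocol 12.1, SAP 4): none.
- Deviations (SAP 5.2): a listing only, with no classification rule and no set built from it.
- Time since onset: no readable section plans a summary. The variables in SAP 5.4 are partly redacted, so this covers visible text only.
- Enrollment (SAP 1 and 4): ended early, with one cohort.

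**The case for a change.** The case for a change runs as follows. The contradiction sits in the eligibility text itself and in unredacted wording. Even if criteria 9 and 10 are accepted in place of 7c, several moments could count (start of oxygen, admission, the test, the first qualifying sign), and these can lie hours or days apart. In the 92-hour example, moving the date by 2 hours reverses eligibility. The deviation listing needs some rule to decide whether such a participant appears in it, and the correction would be a few words in 4.1.1, 4.1.2 and the synopsis plus a sentence in SAP 5.2.

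Most of this description stands: the cross-reference is unreconciled and no section supplies the time. Two parts do not. First, the gap does not cover everyone who enters through the Note, because imaging no older than 72 hours settles exclusion 1 without any further time. Second, the strict reading under which the Note admits nobody is not credible. Criteria 9 and 10 already bind every participant, so naming them makes sense only if they stand in for 7c.

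The case for acting now is weaker still. New eligibility wording cannot affect anyone when enrollment is closed. A dating event chosen afterwards would judge past decisions by a rule the sites did not have, and the times might have to be retrieved from source records. A description of time since onset would be an analysis that the readable plan does not contain.

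**Conclusion.** The gap in wording is real, but it does not call for a change to the plan. It can matter only for participants admitted through the Note whose qualifying image was more than 72 hours old: between 72 and 96 hours if the 24-hour window is kept, and possibly beyond if it is not. The documents do not say how many there were. It may be none, and the single cohort that SAP 1 mentions was planned at about 12.

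For any such participant, the visible consequence is at most a line in a deviation listing, where the uncertainty about onset can simply be noted. No analysis set, planned readable summary or conclusion changes.

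This rests on one qualifying image per participant, on criteria 9 and 10 standing in for 7c, and on the readable text. Some eligibility criteria, schedule rows and baseline variables are redacted, but the Note, criterion 8 and exclusion 1 are not. While recruitment was open, a sentence reconciling the three would have been useful tidying. Now it would bring no gain.

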### Medical History and Comorbid Conditions

10. Hospitalized with at least severe COVID-19 (██████████)
  - a. Positive testing by standard reverse transcription polymerase chain reaction (RT-PCR) assay (or an equivalent COVID-19 test authorized under EUA)
  - b. Symptoms suggestive of severe systemic illness with COVID-19, which could include any symptom of moderate illness or shortness of breath at rest, or respiratory distress
  - c. Clinical signs indicative of severe systemic illness with COVID-19, such as respiratory rate ≥ 30 per minute, heart rate ≥ 125 per minute, oxygen saturation (SpO2) ≤ 93% on room air at sea level or PaO2/FiO2 < 300 mm Hg
11. Serum aspartate aminotransferase (AST) concentration ≤ 120 U/L and serum alanine aminotransferase (ALT) concentration ≤ 150 U/L (approximately 3 × ULN for both parameters)
12. Serum total bilirubin ≤ 1.8 mg/dL, in the absence of Gilbert's syndrome or hemolysis

13. Platelet count  $\geq 120,000/\text{mm}^3$
14. Albumin  $\geq 3.3 \text{ g/dL}$
15. International normalized ratio (INR)  $\leq 1.5$  in the absence of anticoagulant therapy or other coagulopathies

#### ***4.1.2 Exclusion Criteria***

Potential participants will be excluded from the study for any of the following reasons:

##### **ARDS Status**

1. Greater than 72 hours since time of onset of ARDS.
2. Greater than 7 days since start of mechanical ventilation.
3. Unwillingness to follow lung protective ventilation strategy (i.e., tidal volume of 6 mL/kg of predicted body weight and prone positioning) and fluid management protocol (Fluids and Catheters Treatment Trial [FACTT] Conservative or Lite) per local institutional standards. See [Appendix 3](#) for further details.
4. Currently receiving or anticipated to receive extracorporeal life support (ECLS), extracorporeal membrane oxygenation (ECMO) or high-frequency oscillatory ventilation (HFOV).

##### **Medical History and Comorbid Conditions**

5. History of severe chronic respiratory disease with a partial pressure of arterial carbon dioxide ( $\text{PaCO}_2$ )  $> 50 \text{ mm Hg}$  or the use of home oxygen.
6. Major trauma in the prior 5 days.
7. Presence of severe renal impairment, as defined by creatinine clearance  $< 30 \text{ mL/min}$ .
8. Prior or planned lung, liver or bone marrow transplantation.
9. [REDACTED]

10. Suspected or confirmed acute liver failure, as defined by elevations in liver biochemistry, INR or other laboratory markers, with or without clinical symptoms associated with impaired liver function.

11. Suspected or confirmed cirrhosis (compensated or decompensated) as assessed by historical liver histology, imaging, laboratory markers and/or signs and symptoms of portal hypertension and/or hepatic decompensation.

**Prior and Concomitant Medications**

12. [REDACTED]
13. Current treatment or anticipated need for treatment with radiation therapy, cytotoxic or chemotherapeutic agents.
14. Hypersensitivity to PLN-74809 or to any of the excipients, or placebo.

**Screening Assessments**

15. Pregnancy or breastfeeding.
16. Any other clinically significant disorders (e.g., resulting in health care utilization or hospitalization), pre-existing condition, or prior therapy that, in the opinion of the Investigator, would make the participant unsuitable for the study or unable to comply with the dosing and protocol requirements.

**Administrative**

17. Participation in a clinical trial with an investigational agent within 30 days before screening.  
**Note:** Treatment with investigational COVID-19 therapies available under EUA by the FDA and/or off-label use of any other drugs, devices, or interventions that might be used to manage COVID-19 may be allowed, pending review and approval by the Medical Monitor and Sponsor Study Director.
18. Incarceration.

## 5 STUDY DRUG AND ACCOUNTABILITY

### 5.1 Description of Study Drug

#### 5.1.1 *PLN-74809*

[REDACTED]

#### 5.1.2 *Placebo*

A corresponding matching placebo will be provided.

### 5.2 Packaging and Labeling

[REDACTED]

### 5.3 Storage and Accountability

[REDACTED]

The Investigator (or designee) will maintain accurate records of receipt of all investigational drug supplies, including dates of receipt and the amount of study drug that is dispensed and used by each participant. Reasons for departure from the expected dispensing regimen must be recorded. At the completion of the study, all study drugs will be reconciled and destroyed, according to applicable regulations, to satisfy regulatory requirements regarding drug accountability.

### 5.4 Treatment Compliance

Study staff will perform the dosing of the study drug.

## 6 STUDY TREATMENTS

### 6.1 Description of Treatments

- Part 1: 40 mg of PLN-74809 or matching placebo QD
- Part 2: 80 mg of PLN-74809 or matching placebo QD
- Part 3: 160 mg of PLN-74809 or matching placebo QD

[REDACTED]

### 6.2 Dose Modifications and Interruptions

[REDACTED]

[REDACTED]

### 6.3 Selection and Timing of Dose for Each Participant

[REDACTED]

### 6.4 Method of Assigning Participants to Treatment Groups

Approximately 36 participants are planned to be enrolled and centrally randomized according to a computer-generated randomization scheme.

### 6.5 Blinding

[figure not shown]
The PLN-74809 and placebo tablets will be identical in appearance and will be packaged identically to ensure that the participant, Investigator and clinical site staff are unaware of the treatment assignments.

The Sponsor will remain blinded until dosing is completed (i.e., after the last participant enrolled in each study part completes the end of treatment or early termination visit, whichever applies). Selected Sponsor representatives with no direct interactions with clinical sites will subsequently be unblinded to allow for a more comprehensive review and assessment of the safety and PK data by the DSMB before proceeding to subsequent parts of the study.

Procedures will be in place to allow prompt breaking of the blind by the Principal Investigator if needed for the safety management of a participant in the event of a serious adverse event (SAE).

## 6.6 Concomitant Therapy

### 6.6.1 *Allowed Medications*

A large rectangular area of the page has been completely blacked out, obscuring a list of medications. The redaction is irregular, with a jagged right edge and a straight bottom edge.A large rectangular area of the page has been completely blacked out, obscuring a list of medications. The redaction is irregular, with a jagged right edge and a straight bottom edge.

A 20x20 grid of black and white squares. The top row has a black bar at the top. The bottom row has a black bar at the bottom. The rest of the grid is a 20x20 grid of black and white squares.

Treatment with investigational COVID-19 therapies available under EUA by the FDA and/or off-label use of any other drugs, devices, or interventions that might be used to manage COVID-19 may be allowed, pending review and approval by the Medical Monitor and Sponsor Study Director.

#### *6.6.2 Disallowed Medications*

## 6.7 Restrictions

### 6.7.1 *Prior Therapy*

For prior and/or concomitant treatment with COVID-19 investigational treatments or device, see [Section 6.6.1](#). Prior treatment with an investigational treatment within 30 days for other indications is prohibited. Prior radiation therapy is prohibited. Individuals who have received any of these therapies must not be enrolled in the study.

